11.5 Questionnaire administration

All questionnaires will be completed in the clinic by the patient prior to starting study therapy and after completing six weeks of daily Q-Urol/Placebo therapy.

11.6 Dosing and Pain Diary

Patients will be required to keep a diary of the Q-Urol/Placebo doses taken during the study. If a dose is missed or omitted, comments should be added to indicate why the dose was not taken.

Patients will also be required to keep a diary of any medications used for pain management for 28 days after brachytherapy placement. On the diary, subjects will be asked to indicate yes/no if they took any medications for the management of prostate-related pain during the day. They will be asked to record this information daily for 28 days post-brachytherapy.

12 CRITERIA FOR EVALUATION AND ENDPOINT

12.1 Safety

Routine safety and tolerability will be evaluated from the results of reported signs and symptoms, scheduled physical examinations, vital sign measurements, and clinical laboratory test results. More frequent safety evaluations may be performed if clinically indicated or at the discretion of the investigator.

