9 SCHEDULE OF EVENTS

The Schedule of Events table provides an overview of the protocol visits and procedures. Refer to the Study Procedures section of the protocol for detailed information on each assessment required for compliance with the protocol. The Investigator may schedule visits (unplanned visits) in addition to those listed in the Schedule of Events table in order to conduct evaluations or assessments required to protect the wellbeing of the patient. This Schedule of Events will be followed for the entire study.

Version Date: 11APR2023

Table 1: Schedule of Events

	Screening	On Treatment Period						Post-Treatment Period	
Protocol Activities		Day 1	Day 8	Day 15	Day 22	Day 29	Day 36	EOT (Day 43)	30 days post EOT
Visit Window	(-90 days)		(± 2 days)	(± 2 days)	(± 3 days)	(± 3 days)	(± 3 days)	(+7 days)	(± 7 days)
Informed Consent	X								
Demographics	X								
Medical History	X								
Baseline Characteristics ¹	X								
Eligibility Criteria	X								
Randomization	X								
Clinical Assessments				•	•				
Vital Signs ²	X	X						X	
Physical Exam	X	X						X	
ECOG Score ³	X	X							
NCCN Risk Stratification ⁴	X								
Charlson Comorbidity Index ⁵	X								
Phone Call ⁶			X	X	X	X	X		X
Adverse events		X							
Concomitant Medications		X							

Version Date: 11APR2023

	Screening	On Treatment Period					Post-Treatment Period		
Protocol Activities		Day 1	Day 8	Day 15	Day 22	Day 29	Day 36	EOT (Day 43)	30 days post EOT
Visit Window	(-90 days)		(± 2 days)	(± 2 days)	(± 3 days)	(± 3 days)	(± 3 days)	(+7 days)	(± 7 days)
Laboratory Studies									
Hematology ⁷	X								
Chemistry ⁸	X								
Testosterone	X							X	
Inflammatory marker ⁹	X							X	
Subject Materials									
Patient questionnaires ¹⁰	X							X	
Q-Urol/Placebo dosing diary ¹¹		X						X	
Pain management diary ¹²		X						X	
Study Therapy	•								
Q-Urol/Placebo ¹³					X				
Brachytherapy		X							

¹ Appendix 9.

² Vital signs to include weight and height (height will be measured at screening only), blood pressure, pulse rate and temperature.

³ Appendix 11.

Version Date: 11APR2023

⁴ Appendix 8. NCCN Risk Stratification may be taken from the initial consultation note where brachytherapy was recommended.

⁵ Appendix 10.

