⁶ An appropriately trained and delegated study team member will contact subjects on treatment weekly to assess adverse event and concomitant medication information, to answer subject questions, and to ensure compliance with study medication and procedures. 30 days after the last dose of study drug, a study team member will contact subjects to assess adverse event information.

⁷ CBC with differential and platelets.

⁸ Complete Metabolic Panel including: Sodium, Potassium, Chloride, Carbon Dioxide, Alkaline Phosphatase, Aspartate Aminotransferase, Alanine Aminotransferase, Urea Nitrogen, Glucose, Creatinine, Calcium, Protein, Albumin, Bilirubin, Anion Gap.

⁹ Inflammatory markers include: erythrocyte sedimentation rate, C-reactive protein, prostate-specific antigen (PSA)

¹⁰ Questionnaires include: National Institutes of Health-Chronic Prostatitis Symptom Index (NIH-CPSI), The Expanded Prostate Cancer Index Composite (EPIC), The International Prostate Symptom Score (I-PSS), Rectal Function Assessment Score (R-FAS), The Sexual Health Inventory for Men (SHIM) Questionnaire.

¹¹ A Q-Urol/Placebo dosing diary will be dispensed on the day of brachytherapy and returned completed at the EOT visit (Appendix 6).

¹² Patients will be asked to maintain a diary of the daily use of medications taken for prostate pain for 28 days post-brachytherapy (Appendix 7).

¹³ Q-Urol/Placebo will begin after brachytherapy placement.

Version Date: 11APR2023

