11.4 Laboratory Assessments

Samples for all laboratory assessments will be drawn at the time points indicated in the Study Calendar and when clinically indicated. All safety laboratory analyses will be performed by the local laboratory. All safety laboratory assessments must be reviewed by the treating investigator prior to study drug administration.

Table 2: Laboratory Assessments

Laboratory Assessments					
CBC with Platelet Count and Differential	White Blood Cell Count				
	Hemoglobin				
	• Platelets				
	Absolute Neutrophil Count				
	Absolute Lymphocytes				
Complete Metabolic Panel (Chemistry)	Sodium				
	Potassium				
	Chloride				
	Carbon Dioxide				
	Alkaline Phosphatase				

Version Date: 11APR2023

	Aspartate Aminotransferase
	Alanine Aminotransferase
	Urea Nitrogen
	Glucose
	Creatinine
	Calcium
	• Protein
	Albumin
	Bilirubin
Endocrine	Testosterone
Inflammatory Markers	Erythrocyte sedimentation rate
	C-reactive protein
	• Prostate-specific antigen (PSA)

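### Routine safety is to be judged partly from laboratory results, but no haematology or chemistry is scheduled after dosing, so laboratory toxicity is not ascertained systematically in either arm

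*Combined protocol and SAP*

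**What the plan says.** Section 12.1 (Safety) names the sources for routine safety and tolerability: reported signs and symptoms, and "scheduled physical examinations, vital sign measurements, and clinical laboratory test results". It adds that "More frequent safety evaluations may be performed if clinically indicated or at the discretion of the investigator".

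Section 11.4 (Laboratory Assessments) sets the timing: "Samples for all laboratory assessments will be drawn at the time points indicated in the Study Calendar and when clinically indicated". It also states that "All safety laboratory assessments must be reviewed by the treating investigator prior to study drug administration".

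In Table 1 (Schedule of Events), under "Laboratory Studies", the haematology and chemistry rows each carry one mark, at Screening. The rows "Testosterone" and "Inflammatory marker" carry two, at Screening and at EOT (Day 43). Vital signs and physical examination are also repeated at EOT. Section 10.1 allows screening up to 90 days before brachytherapy.

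Objective 1.2.3 asks whether Q-Urol adds toxicity relative to placebo. Its endpoint is the frequency of adverse events by type, CTCAE severity, seriousness, duration and relationship. Section 16.4.1 includes laboratory testing among the ways an adverse event may be detected. It counts an abnormal value as an adverse event only if the value causes signs or symptoms, is judged clinically significant, or needs therapy. Section 16.4.2 gives a similar list of conditions.

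**The concern.** Three of the four safety sources in 12.1 (symptoms, examination, vital signs) are collected from every patient after dosing. The fourth, laboratory results, has no scheduled post-dose blood count or metabolic panel behind it.

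A toxicity comparison between arms depends on the same ascertainment in both. When panels are ordered case by case, the men tested are a selected group. There is then no defined denominator for a rate of abnormality, and no change from baseline can be computed for the arm as a whole. The blind prevents testing from following known assignment, but testing can still follow symptoms. If Q-Urol does reduce symptoms, treated men might be tested less often than placebo men, and laboratory events in the two arms would then be found at different rates for that reason alone.

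The protocol gives its own reasons to want these data. It sets hepatic and renal limits for entry (5.1.5). It warns of additive hypoglycaemic effects and of effects on several metabolic and transport pathways (7.3.3). It describes the trial as assessing safety (4.1) and classifies it as high risk under an IND (16.3). The earlier trials summarised in 2.3 and 3.1.2 are small, and the adverse events listed there are clinical; no laboratory safety results are given.

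**Working it through.** The plan states no figure on this point. The main check is a count of the marks in Table 1, read against 11.4 and 12.1.

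**Scheduled draws per patient (Table 1)**

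| Row | Screening | Day 1 to Day 36 | EOT (Day 43) | 30 days post EOT | Scheduled after first dose |
|---|---|---|---|---|---|
| Haematology | 1 | 0 | 0 | 0 | 0 |
| Chemistry | 1 | 0 | 0 | 0 | 0 |
| Testosterone | 1 | 0 | 1 | 0 | 1 |
| ESR, CRP, PSA | 1 | 0 | 1 | 0 | 1 |

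The number of patients with a scheduled post-dose blood count or metabolic panel is therefore 0 of up to 140. The number with an unscheduled one cannot be known from the documents.

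The EOT draw does not fill the gap. ESR, CRP and PSA are the biomarker endpoint of objective 1.2.2. Neither they nor testosterone report blood counts, liver enzymes, creatinine, glucose or electrolytes.

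**What one EOT panel would add**

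Inputs: 70 patients per arm at full enrolment and 21 per arm at the interim analysis (13.2.1). Assumption: every man in the arm is tested at EOT.

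The probability of seeing at least one case in an arm of n men, when the true rate is p, is 1 − (1 − p)^n. Setting this equal to 0.95 gives p = 1 − 0.05^(1/n).

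- n = 70: p = 1 − 0.05^(1/70) = 1 − 0.958 = 0.042, or 4.2%.
- n = 21 (trial stopped at the interim): p = 1 − 0.05^(1/21) = 1 − 0.867 = 0.133, or about 13.3%.

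If fewer men are tested, these rates rise. They describe the chance of one sighting within one arm. They say nothing about the power to show that the arms differ.

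**The case against.** The strongest reply is that the documents do not contradict themselves. In 12.1 the word for scheduled stands before physical examinations and need not govern laboratory tests. Laboratory results could mean the screening panel plus whatever is clinically indicated. The requirement in 11.4 that safety laboratories be reviewed before study drug is given fits a pre-dose eligibility check, in line with the organ-function limits in 5.1.5. The product is an over-the-counter supplement taken for six weeks, and few adverse events were reported in the earlier quercetin trial. Objective 1.2.3 promises adverse event frequencies, not laboratory shifts, and 16.4.1 would keep many silent shifts out of the endpoint even if they were measured.

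Much of this stands, and it limits the point. A reader might infer that no patient will have any post-dose safety laboratory value, that only men with symptoms would be tested, or that a silent change could never be seen. The documents do not support any of these. Sections 11.4 and 12.1 allow clinically indicated and discretionary tests, discretion does not require symptoms, and 7.3.3 gives reasons for caution in men who have none. Nor does 12.1 promise a comparison of laboratory toxicity by arm.

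The objection does not restore uniform ascertainment. Discretionary testing yields no common denominator, and an asymptomatic value that would be judged clinically significant, and so count under 16.4.1, is found only if someone orders the test. If the panels are meant for eligibility alone, 12.1 should say so.

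**Conclusion.** The point holds in a limited form. Section 12.1 relies on laboratory results for routine safety, yet no haematology or chemistry is scheduled after the first dose for any of the up to 140 patients, and the only scheduled panel may be up to 90 days old at brachytherapy. Post-dose values will come from an unknown and selected subset. Laboratory-detected adverse events are thus not sought systematically, and equal ascertainment in the two arms is not assured. This weakens the between-arm comparison in objective 1.2.3 without invalidating it: clinical adverse events are still collected from everyone, and laboratory findings that come to light are still recorded.

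The conclusion rests on the marks in Table 1 as printed. The neighbouring testosterone, inflammatory marker and questionnaire rows all carry an EOT mark, so the blank cells appear intended. The 4.2% and 13.3% figures assume complete testing at EOT. The primary endpoint and the sample size are unaffected. This is an inexpensive improvement to the safety data.

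**What to change.** Mark haematology and chemistry in the EOT (Day 43) column of Table 1, using the draw already scheduled for testosterone, ESR, CRP and PSA. In 13.2.3, add a summary by arm of change from screening and of CTCAE-graded abnormalities, with the number of men tested as the denominator. Align 11.4 and 12.1 with the revised table.

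The cost is two routine panels per patient, with a little extra work to review results and to grade and follow up any adverse events. No visit or separate blood draw is added. A single Day 43 sample can miss transient changes, and the summary should be presented as descriptive.

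If the panels are not added, reword 12.1 to say that post-dose haematology and chemistry are obtained only when clinically indicated or at the investigator's discretion, and that laboratory toxicity is therefore not systematically compared between arms. It would be inaccurate to say that laboratory toxicity is not assessed at all, because indicated tests are provided for and laboratory-detected adverse events are collected. This alternative costs only a text change, but the data gap remains.

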12.2 Efficacy

The primary outcome variable is the peak score of the National Institutes of Health-Chronic Prostatitis Symptom Index (NIH-CPSI) total score measured from baseline to six weeks post brachytherapy. Efficacy will be determined by the mean difference in outcome variable between the treatment and control groups.

Version Date: 11APR2023

12.3 Population for analyses

12.3.1 Evaluable for toxicity

Subjects who have received one dose of Q-Urol will be evaluable for toxicity.

12.3.2 Evaluable for response

A modified intent-to-treat data set will be used to assess efficacy. Subjects who have successfully undergone brachytherapy and received one dose of Q-Urol will be evaluable for response. Subjects who fail to undergo brachytherapy or begin Q-Urol therapy will be replaced. Those who do not complete the end of treatment patient questionnaires will be considered treatment failures.

12.4 Safety stopping rules

A 5% rate of grade \geq 3 SAEs attributed as definitely or probably related to study drug is considered acceptable, and a 15% rate of grade \geq 3 SAEs attributed as definitely or probably related to study drug is excessive. Excessive toxicity will be evaluated at 10, 21, 30, 40, 50, 60, and 70 patients. Toxicity will be declared excessive if the number of patients with an SAE *exceeds* 2/10, 3/21, 3/30, 4/40, 5/50, 6/60, or 6/70. The stopping boundary was calculated using the "toxbdry" function in the R package "clinfun".

Table 3: Operating Characteristics

Operating Characteristics of Strategy							
True Probability of SAE	Probability the Boundary Will Be Crossed at Any Time	Probability the Trial Will Stop Before the End	Average Sample Size				
5%	10.9%	9.1%	66.4				
7%	29.4%	24.0%	60.9				
9%	52.0%	43.3%	53.5				
11%	71.8%	62.2%	45.6				
13%	85.5%	77.3%	38.5				
15%	93.4%	87.6%	32.6				

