4 STUDY DESIGN

4.1 Description

This is a Phase 2, double-blinded, placebo-controlled trial assessing the safety of Q-Urol use after brachytherapy placement in patients with localized prostate cancer. Patients will be randomized in a 1:1 ratio to receive Q-Urol/Placebo twice daily for six weeks after brachytherapy placement. Questionnaires will be administered pre- and post-treatment to assess the change in prostatitis symptoms and quality of life measures. The mean values between groups will be compared.

Once 42 patients (21 to each arm) have been enrolled and treated on the study therapy, enrollment will be placed on hold and an interim analysis conducted. The interim analysis will be conducted for futility and efficacy and will be reviewed by the DSMC. If the analysis is favorable, as defined in the Statistical Analysis section, the trial will open to the enrollment of 98 additional subjects, 49 per arm. However, if the analysis does not demonstrate standards defined in the statistical analysis, the trial will be closed to accrual.

Version Date: 11APR2023

Safety monitoring will be overseen by the DSMC at HCI. See Section 12.4 for safety monitoring plan and early stopping rules.

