4.3 Number of Patients

The trial will enroll up to 70 patients to each arm, 140 patients total.

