16.3 Data and Safety Monitoring Plan

A Data and Safety Monitoring Committee (DSMC) is established at Huntsman Cancer Institute (HCI) to ensure the well-being of patients enrolled on Investigator Initiated Trials that do not have an outside monitoring review. The roles and responsibilities of the DSMC are set forth in the NCI-approved Data and Safety Monitoring (DSM) plan. The activities of the committee include reviewing adverse events (including SAEs), deviations, important medical events, significant revisions or amendments to the protocol, and approving cohort/dose escalations. If the DSMC and/or the PI have concerns about unexpected safety issues or rising AE trends, the study will be stopped and an unplanned safety data analysis

Version Date: 11APR2023

may take place. Enrollment will not resume until the issues are resolved. The DSMC also reviews and approves audit reports generated by the Research Compliance Office.

This is a Phase II study holding an IND and is classified as high risk per the NCI-approved DSM plan.

Each high-risk study will be assigned a physician member of the DSMC as a medical monitor, or in rare cases, an external medical monitor. The medical monitor will be notified of all serious adverse events (SAEs). All serious adverse events (SAEs) occurring in patients treated at HCI or its affiliates will also be reviewed by the full DSMC monthly.

Each high-risk study will also be assigned a dedicated research compliance officer who will monitor the trial. High-risk studies will be monitored by RCO personnel after the first patient is enrolled and every three months thereafter during active enrollment. The RCO monitor will review the study status and summarize enrollment, toxicities, SAEs, dose-escalation, statistical endpoints (e.g., stopping rules), deviations, etc. for the full DSMC membership at the regularly scheduled meetings. Amendments that increase risk, change dosing, or impact study objectives will be reviewed by the DSMC and approved by the PRMC and IRB. High-risk trials will be formally reviewed by the DSMC after the first patient is enrolled and then quarterly thereafter.

An initial audit of high-risk studies will be conducted by the RCO approximately one year after enrollment begins and annually thereafter. Audits of high-risk studies may be conducted more frequently as requested by the DSMC, IRB, PRMC, RCO management, or the PI.

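### The SAE boundary in section 12.4 acts only at seven patient counts and does not say what follows when the next look's limit is already exceeded between looks

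*Combined protocol and SAP*

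**What the plan says.** Section 12.4 takes a 5% rate of grade 3 or higher SAEs, definitely or probably related to study drug, as acceptable and 15% as excessive. The rule is applied at fixed counts: "Excessive toxicity will be evaluated at 10, 21, 30, 40, 50, 60, and 70 patients". Toxicity is excessive if the number of patients with such an SAE is greater than "2/10, 3/21, 3/30, 4/40, 5/50, 6/60, or 6/70". Table 3 gives the operating characteristics of this seven-look rule. Nothing in 12.4 covers a count that passes the next limit between looks.

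Section 12.4 speaks only of patients. I read these as Q-Urol patients, because section 12.3.1 says "Subjects who have received one dose of Q-Urol will be evaluable for toxicity" and section 4.3 says "The trial will enroll up to 70 patients to each arm, 140 patients total", which matches the last look at 70.

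Section 16.3 provides separate, continuing review. The medical monitor is told of every SAE, and "All serious adverse events (SAEs) occurring in patients treated at HCI or its affiliates will also be reviewed by the full DSMC monthly". The study is stopped if the DSMC or the PI is concerned about unexpected safety issues or an upward trend in adverse events. Section 16.5 requires SAE reports within one business day. Section 8.1 ends study therapy for an individual with a grade 3 or higher SAE attributed to study drug. The only planned accrual hold is in section 4.1, at 42 patients (21 per arm), where "enrollment will be placed on hold and an interim analysis conducted".

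**The concern.** If the count of patients with a qualifying SAE only ever rises, a crossing is settled as soon as the count exceeds the limit for the coming look. The trial's own definition of excessive toxicity is then bound to be met, yet the pre-specified rule stays silent until that look. The reporting timelines already put the information in the DSMC's hands. What is missing is a statement linking the count to the boundary. A DSMC that sees four qualifying SAEs by the 12th patient is not told whether the limit of 3 at 21 patients counts as exceeded.

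At stake is the number of patients treated between the moment the outcome is settled and the moment the formal rule recognises it. This matters most if the true SAE rate is high.

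**Working it through.** **Inputs (section 12.4).** Looks at n = 10, 21, 30, 40, 50, 60, 70. Limits b = 2, 3, 3, 4, 5, 6, 6. Crossing needs a count above b, that is at least 3, 4, 4, 5, 6, 7, 7.

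**Step 1: reproduce Table 3.** Let f(i, c) be the probability of c patients with a qualifying SAE after i patients with no crossing so far. Then f(i, c) = f(i−1, c)(1−p) + f(i−1, c−1)p. At each look, the mass with c > b is removed and counted as a crossing. At p = 5% this gives 10.90% crossing, 9.10% stopping before the end and an average size of 66.45. At p = 15% it gives 93.37%, 87.65% and 32.56. All six rows of Table 3 agree to rounding. Reading the limits as reached rather than exceeded gives 28.2% crossing at 5%, so the word exceeds is the right reading.

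**Step 2: find the longest wait.** In each interval, the earliest patient at which the coming crossing is settled is the previous look plus the larger of 1 and (b + 1 − previous b). For the first look, the previous look and the previous b are both 0.

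| Coming look | Count needed | Earliest settled at patient | Patients left to the look |
|---|---|---|---|
| 10 | 3 | 3 | 7 |
| 21 | 4 | 12 | 9 |
| 30 | 4 | 22 | 8 |
| 40 | 5 | 32 | 8 |
| 50 | 6 | 42 | 8 |
| 60 | 7 | 52 | 8 |
| 70 | 7 | 61 | 9 |

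The maximum is 9. It needs two events in the first 10 patients and then events in patients 11 and 12 (21 − 12 = 9), or six events by patient 60 and then one in patient 61 (70 − 61 = 9).

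**Step 3: find the typical wait.** Each path in the recursion is tagged with the patient k at which the count first exceeds the next limit. The wait is the look minus k, and the average size is recomputed with k in place of the look.

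| True rate | Crossing (both rules) | Mean wait per crossing | Wait of 9, share of crossings | Average size, as written → declared at k |
|---|---|---|---|---|
| 5% | 10.9% | 3.1 | 1.2% | 66.4 → 66.1 |
| 7% | 29.4% | 3.2 | 1.5% | 60.9 → 59.9 |
| 9% | 52.0% | 3.3 | 1.6% | 53.5 → 51.8 |
| 11% | 71.8% | 3.4 | 1.5% | 45.6 → 43.2 |
| 13% | 85.5% | 3.4 | 1.4% | 38.5 → 35.6 |
| 15% | 93.4% | 3.5 | 1.3% | 32.6 → 29.3 |

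As a check, the fall in average size must equal the crossing probability times the mean wait: 0.109 × 3.07 = 0.33 at 5%, and 0.934 × 3.47 = 3.24 at 15%.

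Crossing probabilities are the same because, with a count that cannot fall, a path exceeds a limit before its look only if it also exceeds it at the look.

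**Step 4: the stop-before-the-end column.** With declaration at k, crossings settled at patients 61 to 69 also count as before the end. Only those settled by the 70th patient are left out: 10.90% − 0.25% = 10.65%, or 10.7%, at a 5% rate (Table 3: 9.1%), and 93.37% − 0.49% = 92.88%, or 92.9%, at a 15% rate (Table 3: 87.6%).

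**The case against.** A reader might infer that the plan makes up to 9 further Q-Urol patients be dosed after excessive toxicity is certain. The documents do not support that. Nothing requires dosing to run on to the next look. Section 16.3 gives SAE-by-SAE notification, monthly full-DSMC review and a stop for concern about rising adverse event trends, which fits the worst-case sequence well. The compliance monitor also reports on stopping rules to the DSMC, and under section 4.2 the DSMC knows the treatment assignments. This part of the objection stands: the formal rule is silent between looks, but the trial is not unprotected. What remains is that the section 16.3 stop rests on judgement, has no threshold and does not refer to the 12.4 limits.

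The count can also fall. The boundary uses only events rated definitely or probably related. Section 16.4.1 calls for relationship to be reassessed, and section 16.5 accepts initial reports on incomplete information. An event re-rated before the look would undo a crossing that seemed settled. That stands too, and is why the fix refers to a confirmed count.

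Finally, spaced looks are a disclosed design choice with correctly calculated characteristics. That is right, and no calculation error is alleged. A reader might also want to turn the wait into months, but the documents give no accrual rate, so no calendar figure is offered.

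**Conclusion.** The point holds as an improvement to the monitoring rule. Section 12.4 leaves open whether the boundary is crossed once the next look's limit is exceeded, and section 16.3 does not close the gap. The typical size is about three patients per crossing, and the 9-patient wait has an absolute probability of only 0.1% to 1.2% across true rates of 5% to 15%. Earlier declaration would change the average size by about 0.3 patients at the acceptable rate and 3.2 at the excessive rate, so nearly all the gain falls where the drug is harmful.

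These figures assume that:
- SAEs are known at once and in enrolment order;
- attributions are not revised down;
- the 12.4 counts are Q-Urol patients;
- for the average size, accrual ends when the boundary is declared crossed, as Table 3 assumes at a look.

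With six weeks of dosing and SAE collection for 30 days after the last dose, late events could make the real wait longer or shorter.

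**What to change.** Keep the seven looks and their limits. Add to section 12.4 that the boundary is declared crossed, and referred to the DSMC, as soon as the confirmed number of patients with a qualifying SAE exceeds the limit for the next scheduled look. State there that the counts are of Q-Urol patients, if that is intended. Reconcile this with the between-look review in section 16.3, leaving decisions on accrual and dosing to the sponsor and the DSMC.

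Recalculate two columns of Table 3: average sample size, and the probability of stopping before the end. The crossing column stays as it is.

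The cost is a sentence or two and two table columns, with no extra patients, visits or data. The downside is that an SAE later re-rated as less related could trigger a referral earlier than the scheduled look would have, or one that the scheduled look would not have produced. Requiring a confirmed count limits this.
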